SAP	Statistical Analysis Plan
SD	Standard deviation
STAI-S	State Trait Anxiety Inventory Scale

3 Introduction

Communication is of great importance in all areas of general health and medicine. It can assist and improve medical therapies in order to improve health outcomes. Appropriate use of language and conversations tailored to the individual can help to find the most suitable treatment plan for each patient and to get the patient fit again. Positive suggestions can reduce adverse events like pain, nausea and vomiting.

There are some clues that communication has a positive impact on narcotized patients. Apparently, direct talking to the patient but also tape recordings appear to exert this effect.

3.1 Purpose of the analyses

These analyses will assess the impact of intra-operative therapeutically communication in comparison to a control group on post-operative pain levels, nausea and vomiting of surgical patients.

4 Study Objectives and Endpoints

4.1 Study Objectives

The aim of the study is to find out to what extent intra-operative positive suggestions delivered to a patient during surgery influence post-operative pain. This will be measured through the Numerical Rating Scale (NRS) and the patient's requirement of pain medication.

4.2 Endpoints

Primary endpoint:

Requirement of pain medication (if patient experiences a pain intensity of NRS \geq 3) during the first 2 and 24 hours after surgery.

For evaluation of primary endpoint post-operative pain levels need to be evaluated by NRS at 0 min (admission to PACU), 15 min, 30 min, 45 min, 60 min, 75 min, 90 min, 105 min, 2 hours and 24 hours.

Secondary endpoints:

Maximum post-operative pain levels (NRS) within 2- and 24-hours post-surgery.

Post-operative nausea and vomiting (PONV) at 2- and 24-hours post-surgery.

Requirement of antiemetic medication in presence of post-operative nausea and vomiting (PONV) during the first 2 and 24 hours after surgery.

Post-operative comfort at 2- and 24-hours post-surgery.

Post-operative anxiety at 2- and 24-hours post-surgery.

Post-operative mental orientation grade after extubation, at admission to PACU and at 2- and 24-hours post-surgery.

Anesthesia wakeup time (time from end of surgery until extubation).

5 Study Methods

5.1 General Study Design and Plan

This study is a multicenter, double-blinded, randomized, controlled trial (RCT) of intra-operative therapeutically communication (delivered through headphones of an audio player) versus a control group. Randomization is done by lottery.

	STUDY PERIOD													
	ENROLMENT	RANDOMIZATION	BASELINE	DURING SURGERY	ADMISSION TO PACU	POST-OPERATIVE								
TIME POINT	Prior inclusion	After inclusion	Baseline	Day of surgery	0	15 min	30 min	45 min	60 min	75 min	90 min	105 min	2 h	24 h
ENROLMENT:														
Eligibility screen	Х													
Informed consent	Х													
Randomization		Х												
INTERVENTIONS:														
Audio suggestion				х										
Placebo audio suggestion				Х										
ASSESSMENTS:														
Demographic & medical data			х											
Type of surgery			Х											
HGHSH-5, Apfel score			Х											
Duration of surgery				х										
NRS			Х		Х	Х	Х	Х	Х	Х	Х	Х	Х	Х
Pain medication				х									Х	х
PONV					х	х	х	х	х	Х	Х	Х	Х	х
Wengritzky score													Х	х
Antiemetic medication				х									Х	х
Comfort scale													Х	х
Anxiety (STAI-S)			Х										Х	Х
Mental Orientation				X^1	Х								Х	Х
Anesthesia wakeup time				X^1										

¹ after extubation

5.2 Inclusion-Exclusion Criteria and General Study Population

Inclusion criteria:

Patients who have neurosurgery or abdominal-gynecological surgery: Duration of the surgery should be between 1 to 3 hours and the patient must obtain volatile anesthesia. Moreover, the patient has to be aged between 18 and 70 years and must have a risk of post-operative nausea and vomiting (PONV), measured via the "Apfel-Score", of \geq 2.

Exclusion criteria:

- Massive impairment measured with ASA-Score > 3
- Post-operative requirement of ventilation or requirement of intensive care treatment
- Patients with an epidural catheter
- Patient refuses to participate

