8.1 Protocol Deviations

Major deviations are defined as follows:

- Deviation from main study procedure (audio suggestion) like discontinuation during surgery of more than 10 minutes, wrong treatment in contrast to randomization.
- Violation of inclusion and exclusion criteria.
- Missing informed consent.
- Malfunction of the audio player.
- Unexpected transfer to ICU.

Patients with major deviations will be excluded in the 'per protocol' analysis (see section 7.2).

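### Section 8.1 drops randomised patients from the only planned analysis for events that arise after randomisation: unexpected ICU transfer and, as 5.2 is worded, possibly unplanned ventilation or surgery outside 1–3 h

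*SAP*

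**What the plan says.** - **Order of events.** The schedule in SAP 5.1 puts the eligibility screen before inclusion, randomisation after inclusion, and the audio during surgery. Duration of surgery is recorded only during surgery (5.1) or from its end onwards (5.4).
- **Eligibility (5.2).** "Duration of the surgery should be between 1 to 3 hours" is an inclusion criterion. "Post-operative requirement of ventilation or requirement of intensive care treatment" is an exclusion criterion. Neither is qualified as planned or expected.
- **Major deviations (8.1).** The list includes "Violation of inclusion and exclusion criteria" and, as a separate item, "Unexpected transfer to ICU". The consequence is fixed: "Patients with major deviations will be excluded in the 'per protocol' analysis (see section 7.2").
- **Analysis set (7.2).** Per protocol is the only set. No all-randomised set and no sensitivity analysis is named.
- **Endpoint concerned (4.2).** "Anesthesia wakeup time (time from end of surgery until extubation") is a secondary endpoint.
- **Missing data (7.4).** Missing values are left out of each analysis and reported.

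**The concern.** Randomisation makes the arms comparable at the moment of allocation. Removing patients for something that happens later keeps that comparability only if the event is unrelated to treatment. Need for ICU care or ventilation is part of recovery from anaesthesia, and recovery is what the audio is meant to influence. If the intervention changes how often these events occur, the patients left in the two arms are no longer alike.

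Wake-up time is the most exposed endpoint. It ends at extubation, so the condition that removes a ventilated patient also makes that patient's value very long or unobserved. The patient is lost under 8.1 and, if no extubation time is recorded, again under 7.4. The SAP has no rule for a patient who leaves theatre intubated.

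**Working it through.** **1. Can the exclusion be settled before randomisation?**

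| Ground for exclusion | Source | Known before randomisation? |
|---|---|---|
| Unexpected ICU transfer | 8.1, separate item | No, by its own wording |
| Post-operative ventilation or ICU care | 5.2, through 8.1 | Only if read as planned or expected; the SAP does not say |
| Surgery outside 1–3 h | 5.2, through 8.1 | Only if read as planned; the SAP does not say |

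The first row needs no inference. The other two depend on a reading the SAP leaves open. The case-by-case judgement in 7.2 does not rescue these patients, because 8.1 says that major deviations will be excluded.

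**2. The plan's own sample size.** Inputs from section 6: d = 0.3, two-sided alpha 0.05, 1:1 allocation, power about 80%, total 368. The test behind the figure is not named.

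- t-test: 176 per arm, 352 in total (normal approximation 175 per arm, 350). Neither matches.
- Mann-Whitney, using a t-test with n × 3/π per arm: 184 × 0.955 = 175.7; noncentrality 0.3 × √(175.7/2) = 2.81; power 80.07%. This needs 184 per arm, 368 in total, an exact match.

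The 368 reproduces. The point concerns who is analysed, not the arithmetic.

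**3. Margin for exclusions.** Section 7.1 analyses after 400 patients. 400 − 368 = 32, and 32/400 = 8.0%. The SAP gives no exclusion rate, so the rates below are assumed.

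| Removed | Left | Mann-Whitney power | t-test power |
|---|---|---|---|
| 0% | 400 | 83.2% | 84.9% |
| 5% | 380 | 81.3% | 83.1% |
| 8% | 368 | 80.1% | 81.9% |
| 10% | 360 | 79.2% | 81.0% |
| 15% | 340 | 76.9% | 78.8% |
| 20% | 320 | 74.3% | 76.3% |

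Under a t-test the margin would be 400 − 352 = 48 patients (12%).

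**4. What removal can do to wake-up time.** All rates are assumed; these examples show mechanism, not expected size.

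- *Hiding a difference.* 200 per arm, 1% versus 5% not extubated, times otherwise equal. With these patients excluded, Mann-Whitney rejects in about 5% of simulated trials, so there is no signal. Kept as the longest ranks, it rejects in about 11%. A Fisher test on the counts by arm rejects in about 55%.
- *Shrinking a benefit.* Normal scale, true benefit 0.30 SD, everyone above a common cut removed. The mean below cut c in an arm with mean μ is μ − φ(c − μ)/Φ(c − μ). At c = 1.645 the arm means are −0.109 (control) and −0.362 (intervention), a difference of 0.25. Cuts that remove 2.3%, 5% or 10% of controls (1.1%, 2.6% or 5.7% of the intervention arm) leave 0.27, 0.25 or 0.23 SD.
- *Creating a difference.* No true effect, 200 per arm, 4,000 simulated trials, t-test. Removing the longest 3% of one arm and 7% of the other gives a spurious 0.07 SD and rejection in about 15%. Part of this is the trimming itself: equal removal of 5% in both arms already gives about 7%.

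The examples point in different directions, so the direction of bias cannot be predicted from the SAP.

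**The case against.** Much can be said for the plan.

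- **A reader might infer that 5.2 makes eligibility depend on actual surgery length.** The SAP does not say so. Criteria screened before inclusion are naturally judged on planned length, and the wording is compatible with that. The separate 8.1 item for unexpected ICU transfer would be redundant if 5.2 already covered unplanned ICU care, which suggests that 5.2 means expected care. The protocol, which is not at hand, may settle this. What stands is that the SAP does not say planned and attaches exclusion to any violation.
- **A reader might infer that patients are removed by outcome and that the longest wake-up times all vanish.** ICU transfer and surgery length are not endpoints. A patient extubated late who needs neither ventilation nor ICU stays in, and a patient sent to ICU after prompt extubation has an ordinary wake-up time. Only some values of one secondary endpoint are directly affected.
- **A reader might infer that ICU need cannot appear in the results.** Section 5.4 records adverse events from the end of surgery to 24 h, and section 8 plans listings of all data. ICU need is not invisible. What is missing is a planned count by arm, and section 10 reports only adverse events directly connected to study procedures.
- **Treating staff are blinded (5.3).** This makes deliberate selective exclusion unlikely. It does not prevent selection that arises because the intervention itself changes recovery.
- **The root is the per-protocol-only set in 7.2.** This is so: an all-randomised set would remove most of the problem. It would not supply rules for unextubated patients or for missing pain scores.
- **The longest-rank analysis recovers little.** In the example it misses the difference about nine times in ten. That is why the counts by arm are needed as well.

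**Conclusion.** The point holds in limited form. Following the SAP as written removes randomised patients for unexpected ICU transfer, an event after the intervention has begun, and nothing in the plan restores them. Whether unplanned ventilation and surgery outside 1–3 h do the same depends on wording that 5.2 leaves open. Bias follows only if the intervention affects these events; neither its size nor its direction can be computed, because the SAP gives no rates. The loss of power is modest: none below target up to 32 exclusions (8%), and 76.9% at an assumed 15%, both taking Mann-Whitney as the test behind the 368. The change should be made, but the point does not show that the trial's result would be wrong.

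**What to change.** 1. **5.2:** state that surgery duration and post-operative ventilation or ICU care refer to what is planned or expected before randomisation.
2. **7.2 and 8.1:** make all randomised patients the primary analysis set, with per protocol as a sensitivity analysis. Remove unexpected ICU transfer, unplanned ventilation and actual duration as grounds for exclusion from the primary set. The item on missing consent is a separate matter and is not touched here.
3. **Section 10:** report unexpected ICU transfer and post-operative ventilation as counts by arm.
4. **Wake-up time:** analyse by a rank test, giving patients who leave theatre intubated the longest rank.
5. **Primary endpoint:** 4.2 relies on pain scores from PACU admission, and a patient who goes to ICU may have none. State how such patients enter the analysis, with a sensitivity analysis; otherwise 7.4 drops them again as missing.

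**Cost:** wording in 5.2, 7.2 and 8.1 and a little extra analysis. The price is slightly more variance and a few patients with incomplete pain scores. No treatment or study procedure changes.

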5.3 Randomization and Blinding

Patients are assigned in a 1:1 ratio to intervention or control group by simple randomization technique (drawing lots), for each study center.

This is a double-blinded trial. Assignment to treatment group and conduct of study procedure is performed by independent study personnel, which is not involved in conduct of general anesthesia or post-operative treatment of pain. Medical personnel which is involved in treatment of the patient has no information about group allocation. Headphones of the audio player for therapeutically communication are placed on the ears of patients in control group as well (whereas no audio file will be played).

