On basis of a 1:1 randomization ratio, we calculated that a planned sample of 368 patients would provide the trial with approximately 80% power to detect a difference in postoperative pain therapy on the basis of an effect size of 0.3 at a two-sided alpha level of 0.05. With 5 participating study centers, approximately 70-80 patients need to be included per center.

The sample size calculation is based on a previously published meta-analysis by Rosendahl et al.⁷ Sample size calculation for a power of 80% was done using G*Power software (University Dusseldorf, Dusseldorf, Germany, http://www.psychologie.hhu.de/arbeitsgruppen/allgemeine-psychologie-undarbeitspsychologie/gpower.html).

⁶ Apfel CC, Korttila K, Abdalla M, et al. A Factorial Trial of Six Interventions for the Prevention of Postoperative Nausea and Vomiting. N Engl J Med 2004; 350(24): 2441-51.

⁷ Rosendahl J, Koranyi S, Jacob D, Zech N, Hansen E. Efficacy of therapeutic suggestions under general anesthesia: A systematic review and meta-analysis of randomized controlled trials. BMC Anesthesiol 2016;16(1).

 Caseley-Rondi et al. 1994; d = 0.459
 Korunka et al. 1992; d = 0.405
 Rosenberg et al. 1992; d = 0.384
 Williams et al. 1994; d = 0.323
 Mastropietro et al. 1998; d = 0.315
 Furlong-Read et al. 1993, d = 0.256
 Nilsson et al. 1993; d = 0.244

7 General Considerations

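### Allocation by drawn lots with simple randomisation, unstratified by surgery type and followed by unadjusted pooled tests, leaves avoidable chance imbalance and an undescribed allocation record

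*SAP*

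**What the plan says.** SAP Section 5.1: "Randomization is done by lottery". Section 5.3 gives the detail: "Patients are assigned in a 1:1 ratio to intervention or control group by simple randomization technique (drawing lots), for each study center".

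On who does this, Section 5.3 says "Assignment to treatment group and conduct of study procedure is performed by independent study personnel", and the sentence continues "which is not involved in conduct of general anesthesia or post-operative treatment of pain". It adds: "Medical personnel which is involved in treatment of the patient has no information about group allocation". The schedule in Section 5.1 places randomisation after inclusion, with eligibility screening and consent before it.

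Section 5.2 admits two surgical populations: "Patients who have neurosurgery or abdominal-gynecological surgery". Neither section names surgery type as a stratification factor.

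On size, Section 6 says "With 5 participating study centers, approximately 70-80 patients need to be included per center".

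On analysis, Section 7.6 combines the centres. Section 9, which governs the primary analysis through Section 9.1, names t, Mann-Whitney and chi-squared tests without adjustment. Section 7.3 admits covariates only where applicable, through forward stepwise selection. Neither centre nor surgery type is a fixed model term.

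**The concern.** There are two separate issues.

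**Checking the allocation.** A computer-generated list exists before the first patient, so each assignment can be compared with it. A drawn lot leaves only whatever record is made at the time, and the SAP describes none. The record matters more than usual here. Section 8.1 makes treatment contrary to the randomised arm a major deviation, and Section 7.2 makes the per-protocol set the analysis set. Who is analysed therefore depends partly on knowing reliably which arm was drawn.

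**Balance.** Simple randomisation gives 1:1 only in expectation. With independent draws nothing holds the arms together within a centre or within a surgery type, and the two types may well differ in pain and analgesic need. The trial seeks an effect of 0.3 (Section 6). A chance difference in case mix moves the estimate, and the planned tests have no term to absorb it.

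**Working it through.** **Inputs.** From Section 6: 5 centres, 70-80 patients each, N = 368, effect size 0.3, two-sided alpha 0.05, power about 80%. From Section 5.3: 1:1 simple randomisation. 368 / 5 = 73.6, so 74 is used as the typical centre.

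**1. The plan's own sample size.** A t-test needs 176 per arm (352 in total). Allowing for the Mann-Whitney efficiency of 3/π = 0.955 gives 184 per arm, 368 in total. The noncentrality is 0.3 × √(0.955 × 184 × 184 / 368) = 2.81 and the power is 80.07%. The stated 368 reproduces exactly on that basis.

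**2. Power under an uneven split.** For Binomial(368, 0.5) the 95% range is 165:203. At 165:203 the noncentrality is 0.3 × √(0.955 × 165 × 203 / 368) = 2.80 and the power is 79.7%. Averaged over all splits it is 80.0%. The loss is negligible.

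**3. Imbalance within a centre.** Call a split 60:40 or worse if the larger arm holds at least 60%. With independent draws,

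P = 2 × Σ C(n, k) / 2ⁿ, summed over k ≥ 0.6n,

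and for at least one of five equal centres it is 1 − (1 − P)⁵.

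| Patients in centre | Larger arm at least | 95% range | One centre | Any of five |
|---|---|---|---|---|
| 70 | 42 | 27:43 | 12.0% | 47% |
| 74 | 45 | 29:45 | 8.1% | 34% |
| 80 | 48 | 31:49 | 9.3% | 39% |

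Because counts are whole numbers, P does not change smoothly with n. Over every size from 70 to 80 the lowest value is at 77 (larger arm at least 47): 6.75% in one centre, and 1 − (1 − 0.0675)⁵ = 29.5% in any of five.

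**4. Centre by surgery type.** Assume 37 patients of each type in every centre; the SAP gives no such split. Then P = 18.8% per cell and 1 − (1 − 0.188)¹⁰ = about 87% for at least one of ten cells.

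**5. Effect on the pooled estimate.** Assume half of each surgery type overall and 184 per arm. The between-arm difference in surgery mix has SD √(2 × 0.25 / 184) = 0.052, so its 95% range is ±1.96 × 0.052 = ±0.10. If the types differ by 0.5 SD in outcome (assumption), the typical shift is 0.5 × 0.052 = 0.026 SD and the 95% limit is 0.5 × 0.102 = 0.051 SD. For an assumed difference of 0.3 to 0.8 SD, that limit runs from 0.03 to 0.08 SD. The standard error of the treatment difference is √(2 / 184) = 0.104 SD.

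**The case against.** The case for leaving the text alone has weight.

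- Simple randomisation is a valid method, and the error rate of an unadjusted test already allows for chance imbalance. Step 5 shows a typical shift of about a quarter of a standard error. This stands, and it limits the point to an avoidable inefficiency.
- The 87% depends on an even surgery split in every centre and on asking about any one of ten small cells. The 60:40 threshold is also a choice. Both stand, so the 87% is illustrative only.
- The words on centre in Section 5.3 are ambiguous. If each centre drew without replacement from a fixed 1:1 set and used it up, the centre would be balanced and the table would not apply. But late draws would then be predictable, and that would not be the simple randomisation stated.

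A reader might infer that the allocation cannot be audited, or that an unwelcome draw can be repeated or the patient deferred. The SAP does not support this. It is silent on sealing, recording and replacement, which the protocol may cover. The deviation rule in Section 8.1 presupposes some record of the assigned arm, and the schedule places randomisation after inclusion.

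A reader might also infer that having the same personnel assign and deliver breaks the blinding. Those staff are separate from anaesthesia and pain treatment, and treating staff are not told the arm. Whoever starts the player, or leaves it silent, must know the arm. Nor does the text show that one individual does both tasks. The separation protects care from bias, but it does not conceal or document the draw.

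**Conclusion.** The point holds as a cheap improvement to a stated design choice. The method is set out in both Sections 5.1 and 5.3, so it is not a detail merely left to the protocol.

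The trial is not invalid and loses almost no power (about 0.4 percentage points at the edge of the 95% range). With independent draws, the chance of a 60:40 or worse split in at least one of five centres is about 34-47% at the sizes tabulated, and about 30% at the most favourable size. Neither the randomisation nor the primary analysis deals with centre or surgery type. The likely shift in the estimate is small: about 0.03 SD, assuming an even surgery mix and a 0.5 SD difference between types.

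The weakness in checking assignments is a risk that the SAP leaves open. Nothing in it shows that allocation was or will be compromised.

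**What to change.** 1. In Sections 5.1 and 5.3, replace the lots by a computer-generated list prepared at the coordinating centre, in randomly varying permuted blocks stratified by centre and surgery type. As an illustration, blocks of four would hold the arm difference within any stratum to at most two.
2. Issue it in sequentially numbered opaque sealed envelopes, opened only after inclusion. Keep the list, and compare treatment received with the arm assigned before the deviations in Section 8.1 are judged.
3. In Sections 7.3 and 9.1, prespecify centre and surgery type as fixed covariates in the primary analysis, outside the stepwise selection. Where a rank test is kept, stratify it by the same factors (van Elteren test). Without this step the stratification would not be used in the analysis.

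Cost: one short script in R, which Section 13 already names; envelopes for five centres; and slightly more analysis work. Final blocks may be incomplete in some of the ten strata. No extra patients are needed.

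If recruitment has begun, document how the lots were prepared, drawn (with or without replacement) and recorded at each centre, and make the covariate adjustment in step 3.

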5.4 Study Variables

	Baseline	End of surgery (post extubation)	Post-surgery every 15 min (from admission on PACU until 1 h, 45 mins)	Post-surgery at 2 h after admission on PACU	Post-surgery at 24 h after admission on PACU
History ¹	х				
Age, Sex	х				
NRS ²	х		х	х	х
HGSHS-5 ³	х				
STAI-S ⁴	х			х	х
Apfel ⁵	х				
Duration of surgery		х			x
Intra-operative analgesic drugs ⁶		x			
Intra-operative analgesic co- medication ⁷		х			x
Post-operative analgesic drugs ⁸				х	x
Post-operative analgesic co- medication ⁹				х	x
PONV ¹⁰			х	х	
Wengritzky ¹¹				х	x
Intra-operative antiemetic medication ¹²		х			
Post-operative antiemetic				х	x

	Baseline	End of surgery (post extubation)	Post-surgery every 15 min (from admission on PACU until 1 h, 45 mins)	Post-surgery at 2 h after admission on PACU	Post-surgery at 24 h after admission on PACU
medication ¹³					
Comfort ¹⁴				х	х
Mental Orientation ¹⁵		х	At admission to PACU	х	х
Anesthesia wakeup time ¹⁶		х			
Adverse Events ¹⁷		х	х	х	х

- (1) **History** Medical condition (diseases, medication). Type of surgery.
- (2) **NRS** (Numeric rating scale) Items are measured ranging from 0 to 10 for which 0 = no pain and 10 = worst pain imaginable.¹
- (3) **HGSHS-5** 5-item version of Harvard Group Scale of Hypnotic Susceptibility (ranging from 0 to 5).²
- (4) **STAI-S** State Trait Anxiety Inventory Scale (ranging from 20 to 80).³

¹ Hawker GA, Mian S, Kendzerska T, French M. Measures of adult pain: Visual Analog Scale for Pain (VAS Pain), Numeric Rating Scale for Pain (NRS Pain), McGill Pain Questionnaire (MPQ), Short-Form McGill Pain Questionnaire (SF-MPQ), Chronic Pain Grade Scale (CPGS), Short Form-36 Bodily Pain Scale (SF-36 BPS), and Measure of Intermittent and Constant Osteoarthritis Pain (ICOAP). Arthritis Care Res (Hoboken) 2011;63 Suppl 11(S11):S240-52.

² Bongartz W. German Norms for the Harvard Group Scale of Hypnotic Susceptibility, Form a. Int J Clin Exp Hypn 1985;33(2):131-9.

³ Marteau TM, Bekker H. The development of a six-item short-form of the state scale of the Spielberger State-Trait Anxiety Inventory (STAI). Br J Clin Psychol 1992;31 (Pt 3):301-6.

- (5) Apfel Apfel score of risk for postoperative nausea and vomiting (ranging from 0 to 5).⁴
- (6) Intraop. analgesic drugs Sum of sufentanil dose, sum of fentanyl dose, sum of piritramide dose, sum of metamizole dose, sum of paracetamol dose, sum of COX2-inhibitor (cyclooxygenase 2) dose. Cumulative dosage of non-opioids as percentage of maximum daily dose (maximum daily doses for conversion: metamizole=4000mg, paracetamol=4000mg, ibuprofen=2400mg, diclofenac=150mg).
- (7) **Intraop. analgesic Co-medication** Sum of clonidine dose.
- (8) Postop. analgesic drugs - Sum of opioid dose represented as morphine piritramide=0.7, tilidine=0.2, equivalents (factors for conversion: tramadol=0.1, oxycodone=2.0). Sum of metamizole dose, sum of paracetamol dose, sum of ibuprofen dose, sum of diclofenac dose, sum of COX2-inhibitor (cyclooxygenase 2) dose. Cumulative dosage of non-opioids as percentage of maximum daily dose (maximum daily doses for conversion: metamizole=4000mg, paracetamol=4000mg, ibuprofen=2400mg, diclofenac=150mg).
- (9) **Postop. analgesic Co-medication** Sum of clonidine dose.
- (10) **PONV** (post-operative nausea and vomiting) Items are 'true' or 'false', depending on patient reporting nausea or vomiting within the specified time interval.
- (11) Wengritzky PONV impact scale score (ranging from 0–6), a score of ≥ 5 defines clinically important PONV.⁵
- (12) Intraop. antiemetic medication Sum of granisetron dose, sum of ondansetron dose, sum of dexamethasone dose, sum of droperidol dose.

⁴ Apfel CC, Heidrich FM, Jukar-Rao S, et al. Evidence-based analysis of risk factors for postoperative nausea and vomiting †. Br J Anaesth 2012;109(5):742-53.

⁵ Myles PS, Wengritzky R. Simplified postoperative nausea and vomiting impact scale for audit and post-discharge review. Br J Anaesth. 2012 Mar;108(3):423-9.

- (13) Postop. antiemetic medication Antiemetics Milligram Equivalents
 (ondansetron = 4, dexamethasone = 4, droperidol = 1.25, metoclopramide = 20, dimenhydrinate = 50).⁶
- (14) **Comfort** Scale items are measured ranging from 0 to 10 for which 0 = no comfort and 10 = highest comfort.
- (15) Orientation grade Items are 'full', 'mostly', 'partly' and 'not'. Patients will be asked for their name, location and day of week (3 correct answers = full, 2 correct answers = mostly, 1 correct answer = partly, no correct answer = not).
- (16) Anesthesia wakeup time Time from end of surgery until extubation.
- (17) Adverse events all adverse events during study visits will be documented.

6 Sample Size

On basis of a 1:1 randomization ratio, we calculated that a planned sample of 368 patients would provide the trial with approximately 80% power to detect a difference in postoperative pain therapy on the basis of an effect size of 0.3 at a two-sided alpha level of 0.05. With 5 participating study centers, approximately 70-80 patients need to be included per center.

The sample size calculation is based on a previously published meta-analysis by Rosendahl et al.⁷ Sample size calculation for a power of 80% was done using G*Power software (University Dusseldorf, Dusseldorf, Germany, http://www.psychologie.hhu.de/arbeitsgruppen/allgemeine-psychologie-undarbeitspsychologie/gpower.html).

⁶ Apfel CC, Korttila K, Abdalla M, et al. A Factorial Trial of Six Interventions for the Prevention of Postoperative Nausea and Vomiting. N Engl J Med 2004; 350(24): 2441-51.

⁷ Rosendahl J, Koranyi S, Jacob D, Zech N, Hansen E. Efficacy of therapeutic suggestions under general anesthesia: A systematic review and meta-analysis of randomized controlled trials. BMC Anesthesiol 2016;16(1).

 Caseley-Rondi et al. 1994; d = 0.459
 Korunka et al. 1992; d = 0.405
 Rosenberg et al. 1992; d = 0.384
 Williams et al. 1994; d = 0.323
 Mastropietro et al. 1998; d = 0.315
 Furlong-Read et al. 1993, d = 0.256
 Nilsson et al. 1993; d = 0.244

7 General Considerations

